## 5 STUDY DESIGN

The study will be designed as a prospective surveillance of the immune response to seasonal vaccination in healthy adults of varying ages. A schematic of the study design is shown below:

---

\* Note for children weighing less than 100 lbs, only 15 mL of blood will be drawn at each time point, and plasma will be used for antibody testing. Subjects will be queried regarding any blood being drawn for other purposes such as clinical testing, and that the total drawn will not exceed the above amounts

Influenza season will be defined as when community laboratories detect 4 or more positives in any one week for two weeks in a row. If influenza season has begun subjects will be contacted by phone once every two weeks starting on day 48 and asked about influenza symptoms. Subjects who report symptoms will be asked to return for a clinic visit and specimen collection.

## 6 STUDY POPULATION

The study population will consist of up to 240 medically stable adults and children ages 9 and older enrolled over 5 years. Recruitment will be stratified in an attempt to achieve an even distribution of ages with a goal of 30 subjects in each of 8 age strata (9-19, 20-29...80+)

## 6.1 Inclusion Criteria

Subjects must meet all of the following inclusion criteria to participate in this study:

1. Aged equal to or greater than 9 years of age and weigh at least 50 pounds.
2. The subject must be in good health, as determined by: medical history; and targeted physical examination, when necessary, based on medical history. Stable medical or psychiatric condition is defined as: no recent increase in prescription medication, dose, or frequency of medication in the last 3 months and health outcomes of the specific disease are considered to be within acceptable limits in the last 6 months.
3. The subject is able to understand and comply with the planned study procedures, including being available for all study visits.
4. The subject/parent has provided informed consent/assent prior to any study procedures.
5. Subjects who have not received seasonal flu vaccine for the current year.

## 6.2 Exclusion Criteria

Subjects who meet any of the following exclusion criteria at baseline cannot participate in the study:

1. Subject report of known hypersensitivity to allergy to components of the study vaccine or other components of the study vaccine.
  2. Subject report of known latex allergy
  3. Subject report of a history of severe reactions following previous immunization with licensed or unlicensed influenza virus vaccines.
  4. Subject report of a history of Guillain-Barre syndrome within 6 weeks of receipt of a previous influenza vaccine.
  5. The subject is a female of childbearing potential who is currently pregnant or breastfeeding or intends to become pregnant during the study period between enrollment and 90 days following receipt of vaccine. Pregnancy will be determined by subject interview. Pregnancy testing is not done in this study since there is no increased risk in pregnancy.
  6. The subject is immunosuppressed as a result of an underlying illness or treatment with immunosuppressive or cytotoxic drugs, or use of anticancer chemotherapy or radiation therapy within the preceding 36 months.
-

- 
7. The subject has an active neoplastic disease (excluding non-melanoma skin cancer or prostate cancer that is stable in the absence of therapy) or a history of any hematological malignancy. For this criterion, “active” is defined as having received treatment within the past 5 years.
  8. Have taken high-dose inhaled corticosteroids within 30 days prior to study vaccination.  
*High-dose defined as per age as using inhaled high dose per reference chart*  
<https://www.nhlbi.nih.gov/health-pro/guidelines/current/asthma-guidelines/quick-reference-html#estimated-comparative-daily-doses>
  9. The subject received immunoglobulin or another blood product within the 3 months prior to enrollment in this study.
  10. The subject has received an inactivated vaccine within the 2 weeks or a live vaccine within the 4 weeks prior to enrollment in this study or plans to receive another vaccine within the next 28 days after vaccination.
  11. The subject has an acute or chronic medical condition that, in the opinion of the investigator or appropriate sub-investigator, would render vaccination unsafe or would interfere with the evaluation of responses. These conditions include any acute or chronic medical disease or conditions defined as persisting for 3 months (defined as 90 days) or longer, that would place the subject at an unacceptable risk of injury, render the subject unable to meet the requirements of the protocol, or may interfere with the evaluation of responses of the subject’s successful completion of the study.
  12. Subjects with an active infection or that has an acute illness or an oral temperature greater than 99.9F (37.7C) within 3 days prior to enrollment or vaccination. Subjects who had an acute illness that was treated symptoms resolved are eligible to enroll as long as treatment is completed and symptoms resolved > 3 days prior to enrollment.
  13. The subject is currently participating or plans to participate in a study that involves an experimental agent (vaccine, drug, biologic, device, blood product, or medication) or has received an experimental agent within 1 month prior to enrollment in this study, or expects to receive another experimental agent during participation in this study, or intends to donate blood during the study period.
  14. The subject has any condition that would, in the opinion of the site investigator, place the subject at an unacceptable risk of injury or render the subject unable to meet the requirements of the protocol.
  15. The subject has a history of alcohol or drug abuse in the 5 years prior to enrollment.
  16. The subject has a known human immunodeficiency virus, hepatitis B, or hepatitis C infection.
  17. Subject weighs less than 50 lbs.
-

- 
18. Subject expects to have a medical procedure during the upcoming 8 weeks that estimates blood loss to exceed 400 cc for adults or for children would exceed 3 ml/kg.

### **6.3 Handling of Withdrawals**

Participants who withdraw, or are withdrawn or terminated from the study, or are lost to follow-up after receiving the assigned vaccine will not be replaced. Participants who consented to the study but did not receive the influenza vaccine will be replaced. These subjects will be considered as screen failures.

### **6.4 Termination of Study**

Although the study sponsor has every intention of completing the study, the sponsor reserves the right to terminate the study at any time for clinical or administrative reasons. Reasons for termination include, but are not limited to, study closure due to internal safety review and recommendation, or at the discretion of DMID.

## **7 STUDY INTERVENTION/INVESTIGATIONAL PRODUCT**

### **7.1 Study Product Description**

██████████ Quadrivalent (IIV-4) split virion licensed vaccine produced in embryonated hen's eggs and administered intramuscularly at a dose of not less than 15 ug of HA (as determined by SRID) of the following 4 influenza virus strains (2 A strains and 2 B strains):  
A/Singapore/GP1908/2015 (H1N1) IVR-180 (an A/Michigan/45/2015 [H1N1] pdm09-like virus),  
A/Singapore/INFIMH-16-0019/2016 (H3N2) NIB-104, B/Maryland/15/2016 NYMC BX-69A (a B/Colorado/06/2017-like virus), and B/Phuket/3073/2013.

██████████ Quadrivalent (IIV-4) split virion licensed vaccine produced in embryonated hen's eggs and administered intramuscularly at a dose of not less than 15 ug of HA (as determined by SRID) of the following 4 influenza virus strains (2 A strains and 2 B strains):  
A/Singapore/GP1908/2015 (H1N1) IVR-180 (an A/Michigan/45/2015 [H1N1] pdm09-like virus),  
A/Singapore/INFIMH-16-0019/2016 (H3N2) IVR-186, B/Maryland/15/2016 NYMC BX-69A, (a B/Colorado/06/2017-like virus), and B/Phuket/3073/2013.

### **7.1.1 Acquisition**

Vaccine will be ordered for each influenza season from the University of Rochester Medical Center hospital pharmacy which will acquire the vaccine through distributors.

### **7.1.2 Formulation, Packaging, and Labeling**

### **7.1.3 Product Storage and Stability**

Influenza vaccine will be stored according to manufacturer's directions in secure, limited-access temperature monitored refrigerator environment at 2°C to 8°C (36°F to 46°F) until needed. DO NOT FREEZE. The temperature of the storage unit will be monitored during the duration of the trial, and documentation of proper dedicated storage will be maintained. In the event of accidental deep-freezing or disruption of the cold chain, vaccines will not be administered; and the PI or the responsible person will contact the sponsor for further instructions.

## **7.2 Dosage, Preparation and Administration of Study Intervention/Investigational Product**

Vaccine will be formulated in single dose vials or syringes and will not require additional formulation prior to administration. A vaccine dose of 0.5mL will be administered by a clinical research nurse intramuscularly (IM) in the subject's preferred deltoid (upper arm) per the manufacturer's instructions.

### **7.3 Modification of Study Intervention/Investigational Product for a Participant**

As there is only a single dose administered, there will be no dose or schedule modifications for any subject.

### **7.4 Accountability Procedures for the Study Intervention/Investigational Product(s)**

Records of vaccine receipt and dispensation to the study subject as well as storage and destruction of the vaccine will be maintained according to existing standard operating procedures (SOPs)

### **7.5 Assessment of Participant Compliance with Study Intervention/Investigational Product**

Not applicable, single intervention within the vaccine clinic only.

### **7.6 Concomitant Medications/Treatments**

Administration of any medication or therapies considered necessary for the subject's welfare will be recorded and documented in the subject's source documentation. Concomitant medications will include all medications taken within 30 days prior to enrollment through 62 days post vaccination or early termination, whichever occurs first.

The following criteria will be reviewed with the subject's during each follow up visit. If any of these become applicable during the study, it will be noted in the subject's record.

1. Use of any investigational drug or investigational vaccine other than the study article.
2. Administration of chronic (defined as more than 14 days) immunosuppressants or other immune-modifying drugs (topical and nasal steroids are allowed).
3. Receipt of a licensed vaccine.
4. Receipt of immunoglobulins and/or any blood products.

---

## 8 STUDY SCHEDULE

### 8.1 Vaccination/Baseline (Defined as Day 0)

At the baseline visit, subjects will be enrolled in the study and if they meet the entry criteria will receive influenza vaccine. The following procedures will be performed at the baseline visit.

- The study will be explained to the subject/parent, and the informed consent document will be signed. Subjects/Parents will keep a signed copy of the informed consent for their information. Subjects 9 to 12 will be read an Assent Script and subjects 13-17 will sign an Assent Form.
- A medical history will be obtained including history of prior Influenza vaccinations, and details recorded in the case report form.
- Concomitant medications will be reviewed and recorded.
- A targeted physical examination will be performed, if indicated by the medical history, directed at the relevant portions of the exam.
- The entry criteria will be reviewed and it will be verified that the subject meets all entry criteria. If the subject does not meet the entry criteria, the subject will be discontinued from the study, or can be rescreened in the case of entry criteria mandating temporary delays.

Subjects will be considered enrolled if they have signed the consent form. However, only subjects who meet the entry criteria will be vaccinated and continue in the study. The reasons for screen failure will be recorded for all subjects who do not meet the entry criteria. If the entry criteria are met:

- 30 mL of blood will be obtained from an arm vein (3 x 10 mL green top tubes) for isolation of Peripheral Blood Mononuclear Cells (PBMC).
- 8 mL of blood will be obtained from an arm vein (1 x 8 mL red top tube) for serum.
- For children who weigh less than 100 lbs, only 15 mL of blood will be drawn
- Subjects will receive vaccine by intramuscular injection in open label fashion.

- 
- Subjects will be observed in the clinic for 30 minutes post vaccination for development of acute adverse events

## **8.2 Follow-up and Final Visits**

### **8.2.1 Day 7 visit (+/- 1 day)**

Subjects will return one week after vaccination for the day 7 visit. Because the timing of assessment of the cellular response to vaccination is critical, every effort will be made to ensure that subjects return on day 7. Visits that occur out of window will still be evaluated but will not be included in the primary analysis. On the day 7 visit, the following procedures will be done:

- Interval medical history will be obtained including concomitant medications, reviewing any new events since the last visit.
- The site of vaccination will be examined. If indicated by medical history, a directed physical exam will also be performed.
- Any adverse events (AE) will be recorded and appropriate corrective actions taken if indicated.
- 30 mL of blood will be obtained from an arm vein (3 x 10 mL green top tubes) for isolation of Peripheral Blood Mononuclear Cells (PBMC).
- 8 mL of blood will be obtained from an arm vein (1 x 8 mL red top tube) for serum.
- For children who weigh less than 100 lbs, only 15 mL of blood will be drawn

### **8.2.2 Day 28 visit (+/- 3 days)**

Subjects will return for follow up approximately 28 days after vaccination for assessment of the immune response. At that visit, the following procedures will be performed:

- Interval medical history will be obtained including concomitant medications, reviewing any new events since the last visit.
- If indicated by medical history, a directed physical exam will also be performed.

- Any adverse events (AE) will be recorded and appropriate corrective actions taken if indicated.
- 30 mL of blood will be obtained from an arm vein (3 x 10 mL green top tubes) for isolation of Peripheral Blood Mononuclear Cells (PBMC).
- 8 mL of blood will be obtained from an arm vein (1 x 8 mL red top tube) for serum.
- For children who weigh less than 100 lbs, only 15 mL of blood will be drawn

### **8.2.3 Day 90 visit (+/- 7 days)**

Subjects will return approximately 90 days after vaccination for a final follow-up visit. At this visit the following procedures will take place:

- Interval medical history will be obtained, including concomitant medications, reviewing any new events since the last visit.
- If indicated by medical history, a directed physical exam will also be performed.
- Any adverse events (AE) will be recorded and appropriate corrective actions taken if indicated.
- 30 mL of blood will be obtained from an arm vein (3 x 10 mL green top tubes) for isolation of Peripheral Blood Mononuclear Cells (PBMC).
- 8 mL of blood will be obtained from an arm vein (1 x 8 mL red top tube) for serum.
- For children who weigh less than 100 lbs, only 15 mL of blood will be drawn

### **8.2.4 Blood Volumes in Children**

The blood draws in this protocol will impose an upper limit of 3 mL/kg over any 8-week period for all pediatric patients. This volume remains well below the allowed upper limit of 10% of total blood volume in an 8-week period as minimal risk. From healthy subjects who weigh at least 100 pounds, the total amount of blood drawn in any 8 week period is 38 x 3, or 114 mL. For subjects who weigh less than 100 lbs, the total blood drawn will be 45 mL. Neither of these amounts will exceed the limit of 3 mL/kg

---

### **8.2.5 Surveillance for acute influenza**

Influenza season will be defined as when community laboratories detect 4 or more positives in any one week for two weeks in a row, and will end when influenza is no longer detected. During influenza season, subjects will be contacted by phone every other week to enquire about influenza like symptoms. Subjects who report symptoms meeting the case definition of influenza (fever or feverishness plus either cough, rhinitis, or sore throat on the same or consecutive days) will be asked to return for an acute illness visit. At this visit the following procedures will take place

- Interval medical history will be obtained, including concomitant medications, reviewing any new events since the last visit.
- The presence and severity of respiratory symptoms will be assessed and recorded using a visual analog scale.
- A combined nasal and throat swab will be obtained for rtRT-PCR detection of influenza virus.
- If positive, the subject will be invited to participate in the Acute Flu study (DMID 14-0101) to assess the immune response to infection

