**Schematic of Study Design:**

\* Note: For children weighing less than 100 lbs, only 15 mL of blood will be drawn at each time point and plasma will be used for antibody testing. Subjects will be queried regarding any blood being drawn for other purposes such as clinical testing, and that the total drawn will not exceed the above amounts

In addition, beginning on day 48, subjects will be contacted by phone once every two weeks during the influenza season and asked about influenza symptoms. Subjects who report symptoms will be asked to return for a clinic visit and specimen collection. Influenza season will be defined as when community laboratories detect 4 or more positives in any one week for two weeks in a row.

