### Secondary Outcome Measures

- Description of demographic and clinical characteristics and immune response to vaccination among subjects who develop symptomatic influenza (Vaccine Failures) and among subjects who do not.

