## 19 SUPPLEMENT/APPENDICES

Table of procedures by visit and study day								
	V1	V2	V3		V4			
Procedure	D0	D7	D28	D48, D62, D76	D90	D104	D118, D132, D146, D160, D174, D188	Flu** Illness
Informed Consent	X							
Medical History	X							
Interim History		X	X		X			X
Concomitant Meds	X	X	X		X			X
Targeted physical exam*	X	X	X		X			X
Review Enrollment Criteria	X							
Peripheral blood (mL)***	38	38	38		38			
Administer Vaccine	X							
30 minute observation	X							
Review Adverse Events	X	X	X					
Flu surveillance phone call				X		X	X	
NP swab for flu PCR								X

*As indicated by symptoms or history            Visits in italics occur only during influenza season (see protocol for definition)            ** Subjects reporting flu-like symptoms will be asked to make an influenza visit            *** Blood drawing in children will not exceed 3 mL/kg in any 8 week period

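### Finding influenza by a call every two weeks, with no prompt to report at onset, delays the swab and can lose PCR-confirmed cases from an already small vaccine-failure group

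*Combined protocol and SAP*

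**What the plan says.** **Contact.** Section 8.2.5 provides that, in season, "subjects will be contacted by phone every other week to enquire about influenza like symptoms". The schematic note in Section 1 agrees ("subjects will be contacted by phone once every two weeks during the influenza season", from day 48), as does Section 5. The procedures table in Section 19 places calls at D48, D62, D76, D104 and then "D118, D132, D146, D160, D174, D188". The D90 visit takes the slot between D76 and D104. It has an interim history, but neither a surveillance call nor a swab is marked for it.

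**Trigger and test.** Section 5 says: "Subjects who report symptoms will be asked to return for a clinic visit and specimen collection". Section 8.2.5 makes the trigger a symptom definition: "fever or feverishness plus either cough, rhinitis, or sore throat on the same or consecutive days". At the illness visit, "A combined nasal and throat swab will be obtained for rtRT-PCR detection of influenza virus". The only stated use of the result is that a positive subject is invited into a separate acute influenza study, DMID 14-0101. Nothing is said about a negative result.

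**Endpoint.** The secondary outcome in Section 4.2 describes characteristics and immune response "among subjects who develop symptomatic influenza (Vaccine Failures) and among subjects who do not". It does not mention laboratory confirmation. Section 12.4 gives only the timing of the analysis and has no rule for classifying illnesses.

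**What is not stated.** The protocol text does not tell subjects to contact the site when symptoms begin. It does not call for an onset date and sets no limit on the time from onset to swab. Section 8.4 allows unscheduled visits and further laboratory tests, but lists no influenza swab among them.

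**The concern.** A PCR swab confirms influenza only while virus can still be detected. A plan that waits for the next two-weekly call builds a delay into the swab, and that delay is avoidable because the subject knows of the illness on the first day.

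Both parts of the secondary objective are affected. The first concerns factors related to vaccine failure. In a cohort of at most 240 the number of influenza cases will be small, so each case that loses its confirmation matters. The second concerns the immune response to infection in vaccinated subjects. A positive PCR is the written condition for the invitation to the follow-on study, so a true case swabbed too late gets no invitation, however failure is defined.

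Without an onset date, the analyst cannot tell a negative swab that argues against influenza from one that was simply taken late. Onset dates not collected at the time may not be reliably recovered afterwards.

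**Working it through.** **1. Is there a figure to reproduce?** No. The documents give no attack rate, case count, PCR sensitivity or onset-to-swab delay for influenza. The precision table in Section 12.2 concerns memory B cells in strata of 30 and does not bear on this point.

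**2. Contact interval.** The contact days in Section 19 are 48, 62, 76, 90 (visit), 104, 118, 132, 146, 160, 174 and 188. Every step is 14 days. Counting the D90 visit as a contact is the favourable reading. On marked calls alone, D76 to D104 is 28 days.

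**3. Delay from onset to swab.** Assume onset is uniform over the 14 days between contacts, the call alone finds the illness, and the visit follows the call by L days.

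- Onset to call: mean 14/2 = 7 days, maximum 14.
- Onset to swab: mean 7 + L, so 7 to 10 days for L = 0 to 3.
- Share swabbed more than 7 days after onset: (14 + L − 7)/14, which is 7/14 = 50% at L = 0 and 10/14 = 71% at L = 3.

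**4. Share of cases still PCR-detectable.** Assume positivity lasts d days and then stops. The share is (d − L)/14.

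| Assumed d (days) | L = 0 | L = 2 |
|---|---|---|
| 4 | 4/14 = 29% | 2/14 = 14% |
| 7 | 7/14 = 50% | 5/14 = 36% |
| 10 | 10/14 = 71% | 8/14 = 57% |
| 14 | 14/14 = 100% | 12/14 = 86% |

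**5. What this means in cases.** Take all 240 subjects, assumed attack rates of 2%, 5% and 10%, L = 1, and no self-reporting. The share missed is (14 + 1 − d)/14: 36% at d = 10, 57% at d = 7 and 71% at d = 5.

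| Attack rate | True cases | Missed, d = 10 | Missed, d = 7 | Missed, d = 5 |
|---|---|---|---|---|
| 2% | 240 × 0.02 = 4.8 | 1.7 | 2.7 | 3.4 |
| 5% | 240 × 0.05 = 12 | 4.3 | 6.9 | 8.6 |
| 10% | 240 × 0.10 = 24 | 8.6 | 13.7 | 17.1 |

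If half of ill subjects report promptly of their own accord, these losses halve.

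**6. Dilution of the comparison group.** Suppose failure required a positive PCR and every missed case sat among the non-failures. The true cases in that group would then be missed/(240 − cases + missed). The lowest value is 1.7/(235.2 + 1.7) = 0.7% and the highest 17.1/(216 + 17.1), about 7%. With half self-reporting, the low end falls to about 0.4%.

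**The case against.** **Classification.** A reader might infer that late PCR-negative subjects are counted as non-failures, and that the contrast between the groups is therefore biased towards no difference. The documents do not support this. Failure is described only as symptomatic influenza, the case definition in Section 8.2.5 consists of symptoms, and the PCR result has no stated role in the endpoint. A negative illness could be classed either way. If symptoms suffice, a late swab removes nobody from the failure group, but other febrile respiratory illnesses can enter it. Even if PCR were required, step 6 shows that dilution of the large group is slight. What stands is that the rule is missing, and that lost invitations to the follow-on study do not depend on it.

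**Route to a swab.** A reader might also infer that the call is the only way to be swabbed. Section 8.4 permits unscheduled visits at any time, the footnote in Section 19 offers an illness visit to anyone reporting symptoms without tying it to a call, and the D90 visit takes a history. The consent form and the Manual of Procedures are not in the available text, and either could tell subjects to call if ill. These are fair points. Still, they describe permissions or possibilities. The two-weekly call is the only planned contact that actively looks for illness, and the protocol text does not prompt earlier reporting.

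**Size.** The detectable share runs from 14% to 100% and depends on an assumed duration of positivity, a sharp cut-off and no self-reporting. That is correct, and no single loss should be quoted.

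**Importance.** The endpoint is secondary and descriptive, with no planned test or power calculation. The primary HAI and MN endpoints do not depend on it.

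**Conclusion.** The concern holds in a limited form. As written, surveillance places the call 7 days after onset on average and up to 14, and the plan neither shortens nor records that delay. For assumed positivity of 4 to 14 days, between 29% and 100% of call-detected cases remain detectable with a same-day swab, and between 14% and 86% with a 2-day lag. This rests on uniform onset between contacts, detection by the call alone, and D90 counted as a contact. Spontaneous early reporting would reduce the loss.

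The main consequence is fewer PCR-confirmed cases in a group that may number only about 5 to 24, and fewer subjects eligible for the infection-response study. Contamination of the non-failure group is minor. Whether failure needs a positive PCR, and how a late negative is classed, is an open gap. It should not be read as a rule that late negatives are non-failures. The point warrants a change to the protocol but does not threaten the primary analysis.

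**What to change.** 1. In Section 8.2.5, add that subjects are instructed at enrolment to phone the site when symptoms begin during the season. Keep the two-weekly call as a backstop. More frequent calls are not needed.
2. Record the date of symptom onset at the illness visit and derive the days from onset to swab.
3. In Sections 4.2 and 12.4, define vaccine failure as PCR-confirmed symptomatic influenza. State in advance an interval from onset beyond which a negative swab is uninformative, and class illnesses with such a swab as undetermined. Add a sensitivity analysis that excludes them from the non-failure group.
4. A rise in HAI titre from day 28 to day 90 may be used as supporting evidence, but only for illness before day 90. Seven of the ten call dates (D104 to D188) fall after the last scheduled blood draw, and the rise says nothing about illness in that period.

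The cost is one instruction at enrolment, one date field, a short definition in the analysis section and a few more illness visits.
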